7.3.4 Regulatory Reporting Requirements for Serious Adverse Events

The investigator is required to promptly (ie, within 24 hours) notify the Sponsor of the occurrence of an SAE, so that legal and ethical obligations towards the safety of participants and the safety of a study drug under clinical investigation are met.

The Sponsor has a legal responsibility to notify both the local regulatory authority and other regulatory agencies about the safety of a study drug under clinical investigation. The Sponsor will comply with country-specific regulatory requirements relating to safety reporting to the regulatory authority, Institutional Review Boards (IRB)/Independent Ethics Committees (IEC), and investigators.

Investigator safety reports must be prepared for suspected unexpected serious adverse reactions (SUSARs) according to local regulatory requirements and Sponsor policy and forwarded to investigators as necessary.

An investigator who receives an investigator safety report describing an SAE or other specific safety information (eg, summary or listing of SAEs) from the Sponsor will review and then file it along with the IB and will notify the IRB/IEC, if appropriate, according to local requirements.

7.3.5 Notification of Pregnancy

Because all participants are required to have a boost immunization of trivalent inactivated IPOL™, risk of lerapolturev transmission from mother to fetus after intratumoral injection is expected to be limited. Because risk is unknown, all participants will be required to utilize contraception during receipt of lerapolturev injections. In addition, use of PD-1 inhibitors may increase risk of fetal harm when administered to pregnant women. Women should be advised of the potential risk to a fetus and to use effective contraception during treatment with anti-PD1 therapy and for 150 days after the last dose received.

Confidential Page 78 of 109

Details of all pregnancies in female participants and female partners of male participants will be collected after the start of study drugs and until 150 days after the last dose. If a pregnancy is reported, the investigator should inform the Sponsor within 24 hours of learning of the pregnancy.

Abnormal pregnancy outcomes (eg, spontaneous abortion, fetal death, stillbirth, congenital anomalies, ectopic pregnancy) are considered SAEs.

7.4 Tissue and Blood-Based Biomarker and Cytokine Analyses

Tissue Biopsy Collection: Participants are required to submit a baseline tumor biopsy to enroll in the study. Submission of archival tissue is allowed if collected within 4 months prior to Cycle 1, Day 1, and the participant received no intervening systemic/intratumoral anti-cancer therapy between biopsy collection and Cycle 1, Day 1 (eg, focal RT of non-biopsied lesions is allowed). If no archival tissue meeting these requirements is available, a baseline tumor biopsy should be collected during the Screening Period. During study participation, mandatory biopsies should be collected from injected lesions, non-injected lesions, and draining lymph nodes per the corresponding SOA (Table 1 and Table 2 [Arm 2: lerapolturev + nivolumab]). For participants in Arm 1 that crossover to Arm 2, additional mandatory biopsies of an injected lesion, non-injected lesion, and draining lymph node should be performed at the time of crossover and on treatment as described in the treatment group's SOA (Table 1 and Table 2 [Arm 2: lerapolturev + nivolumab]).

At all timepoints, biopsies from all three sites (injected lesion, noninjected lesions and draining lymph nodes) should be collected if the biopsy is technically feasible and does not put the participant at significant risk. Examples of biopsy sites considered to be of significant risk include, but are not limited to the following: biopsies of the brain, lung, mediastinum, pancreas, or endoscopic procedures extending beyond the esophagus, stomach, or bowel wall. For those situations where the investigator determines biopsy of a lesion would (1) lead to a significant decrease in the size of the lesion such that response assessment by RECIST 1.1 would be confounded, or (2) increase the risk of lerapolturev leakage from the lesion, the mandatory biopsy for that timepoint can be waived. In addition, complete resection of target lesions is prohibited unless necessary for participant's safety as determined by the investigator.

Tissue samples may be analyzed by immunohistochemical staining, RNA and/or DNA sequencing, and other molecular techniques to confirm the presence of lerapolturev, and to determine the presence or absence of biomarkers that may (1) predict response to lerapolturev, (2) measure the associated immune response and/or changes in immune cell function over time, or (3) to further characterize lerapolturev's mechanism of action. Samples (blood and tissue) may be stored and used for future research for up to 10 years.

Blood Biopsy Collection: Mandatory blood samples should be drawn during the screening period and while on study, as described in the appropriate SOA (Table 1 and Table 2

Confidential Page 79 of 109

[Arm 2: lerapolturev + nivolumab]), to facilitate evaluation of immune cell function and cytokine profiles before and after study treatment administration. Participants in Arm 1 who crossover to Arm 2 should also have blood samples collected at the time of crossover and on treatment as described in the requisite SOA (Table 1 and Table 2 [Arm 2: lerapolturev + nivolumab]). In addition, an additional sample is to be drawn in the event any participant (regardless of treatment arm) experiences an AESI of CRS or ICANS. This sample should be drawn as soon as possible after learning of the event, to facilitate the interrogation of potentially relevant changes in circulating cytokine levels.

Blood samples may be interrogated by cytokine and flow cytometric analyses, RNA and/or DNA sequencing, and other molecular techniques to evaluate signatures of antitumor immune response to lerapolturev in circulation. In addition, various immune cell types, including peripheral blood mononuclear cells, may be isolated and assayed via genetic and proteomic techniques to evaluate any changes in cell function following treatment with lerapolturev with or without concurrent anti-PD-1. These samples will be stored under the appropriate conditions as described in the laboratory manual and analyzed as a group by the Sponsor or designee at designated intervals. Samples (blood and tissue) may be stored and used for future research for up to 10 years.

8 STATISTICAL CONSIDERATIONS

8.1 Stratification Factors

Participants receiving lerapolturev injections using the **Q3/4W** schedule ± anti-PD-1 therapy will be stratified based on time since prior anti PD-1/L1 exposure (≤6 weeks versus >6 weeks) and baseline LDH (normal versus >ULN).

Participants receiving lerapolturev injections using the **QW** schedule ± anti-PD-1 therapy will be stratified based on type of anti-PD-1/L1 resistance (primary versus secondary as defined in Kluger et al⁷) and baseline LDH (normal versus >ULN).

8.2 Statistical Hypotheses

Lerapolturev administered in combination with anti-PD-1 therapy on the **QW** injection schedule to participants with anti-PD-1 refractory melanoma will result in an ORR of ≥ 33%.

8.3 Sample Size Determination

The determination of sample size in this two-arm, randomized open-label Phase 2 trial was based on feasibility and logistical considerations. As discussed in Section 1.1, the Sponsor estimates that the true activity of anti-PD-1 re-challenge in the anti-PD-1 refractory population eligible for this study is less than 10%. Therefore, lerapolturev administered in combination with anti-PD-1 therapy using the **QW** injection schedule, will be considered to have anti-tumor activity in the anti-PD-1 refractory melanoma population

Confidential Page 80 of 109

if the lower bound of the 95% CI is above 10%. We estimate the sample size for participants receiving lerapolturev (**QW** schedule) ± anti-PD-1 therapy to be approximately 30 participants (n=15 per arm). Therefore, 5 of 15 participants (ie, 33%) in Arm 2 treated with the lerapolturev/anti-PD-1 combination (**QW** schedule) must have an objective response for the 95% CI to be greater than 10% (95% CI: 11.8% to 61.6%).

Additional comparisons (eg, Arm 1 versus Arm 2; Q3/4W schedule vs QW schedule for each Arm etc.) are planned. However, no formal hypothesis will be tested. Additional detail will be provided in the statistical analysis plan (SAP).

8.4 Populations for Analyses

For participants receiving the **QW** schedule of lerapolturev injections, enrollment will be stratified based on baseline LDH levels (normal versus >ULN) and type of anti-PD-1/L1 resistance (primary versus secondary), primarily for the purpose of balancing key participant descriptors between the treatment arms. For purposes of analysis, the following key populations are defined; additional populations may be defined in the SAP:

Population	Description
Intent-to-treat	All participants who sign the ICF and are randomized
Efficacy QW Schedule	Participants receiving at least one lerapolturev injection on the QW schedule and at least 1 post-baseline evaluation
Efficacy—Q3/4W Schedule	Participants receiving at least one lerapolturev injection on the Q3/4W schedule and at least 1 post-baseline evaluation
Crossover	Participants from Arm 1 receiving at least one lerapolturev injection with concurrent anti-PD-1 and at least 1 post-crossover evaluation
Safety—QW	Participants receiving at least one lerapolturev injection on the
Schedule	QW schedule
Safety—Q3/4W	Participants receiving at least one lerapolturev injection on the
Schedule	Q3/4W schedule

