An overall summary of AEs can be found in Table 3. No DLTs, lerapolturev AEs of special interest, treatment-related Grade ≥3 AEs, treatment-related SAEs, or Grade 5 AEs regardless of relationship were reported. The most common (of total participants) AEs regardless of relationship were vomiting (17.6%), constipation (11.8%), fatigue (11.8%), hypertension (11.8%), nausea (11.8%), pain in extremity (11.8%), pyrexia (11.8%), and tumour pain (11.8%). The only AE related to lerapolturev that was reported in more than 1 participant was fatigue, which was observed in 2 participants (11.8%) (Table 4). There were no Grade ≥3 AEs that occurred in more than 1 participant and none were related to either lerapolturev or anti-PD-1 therapy. No participant reported symptoms of CRS or immune effector cell associated neurotoxicity syndrome (ICANS). (Table 3). With regards to efficacy, the best anti-tumor responses observed as of the data cutoff have been stable disease. Together, these data suggest further optimization of the lerapolturev dose and/or schedule may be required to rekindle immunotherapy responsiveness in the truly refractory population. For more information, consult the IB.

Confidential Page 38 of 109

Table 3. LUMINOS-102 Overall Summary of Adverse Events as of 10DECEMBER2021

Summary	Lerapolturev Monotherapy, Safety Run-in ¹ (N=6)	Lerapolturev Monotherapy (Arm 1) ¹ (N=5)	All Lerapolturev Monotherapy 1 (N=11)	Lerapolturev/ Anti-PD-1 (Arm 2) (N=6)	All Participants ¹ (N=17)	Crossover ² Lerapolturev Monotherapy to Lerapolturev/Anti- PD-1 (N=7)	All Lerapolture v/ Anti-PD-1 (N=13)
Participants with one or more AEs, n (%)	6 (100.0%)	2 (40.0%)	8 (72.7%)	2 (33.3%)	10 (58.8%)	5 (71.4%)	7 (53.8%)
Participants with one or more treatment-related ³ AEs, n (%)	4 (66.7%)	1 (20.0%)	5 (45.5%)	2 (33.3%)	7 (41.2%)	2 (28.6%)	4 (30.8%)
Lerapolturev-related AEs, n (%) Anti-PD-1-related AEs, n (%)	4 (66.7%) NA	1 (20.0%) NA	5 (45.5%) NA	1 (16.7%) 1 (16.7%)	6 (35.3%) 1 (5.9%)	2 (28.6%) 2 (28.6%)	3 (23.1%) 3 (23.1%)
Participants with one or more serious AEs, n (%)	0 (0.0%)	0 (0.0%)	0 (0.0%)	1 (16.7%)	1 (5.9%)	0 (0.0%)	1 (7.7%)
Total number of serious AEs, n	0	0	0	3	3	0	3
Participants with one or more treatment-related³ serious AEs, n (%) Lerapolturev-related serious AEs,	0 (0.0%)	0 (0.0%)	0 (0.0%)	0 (0.0%)	0 (0.0%)	0 (0.0%)	0 (0.0%)
n (%) Anti-PD-1-related serious AEs,	0 (0.0%)	0 (0.0%)	0 (0.0%)	0 (0.0%)	0 (0.0%)	0 (0.0%)	0 (0.0%)
n (%)	NA	NA	NA	0 (0.0%)	0 (0.0%)	0 (0.0%)	0 (0.0%)

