Participant is receiving weekly injections	< 6 months from Cycle 1 Day 1	Continue QW injections for a total of 7 (monotherapy + combination) followed by Q3W dosing (pembrolizumab) or Q4W dosing (nivolumab)*
Participant is receiving injections Q3W (pembrolizumab) or Q4W (nivolumab)	< 6 months from Cycle 1 Day 1	Continue concurrent dosing schedule

Schedule of lerapolturev monotherapy injections at the time of crossover	Timing of when criteria for crossover are met	Recommended lerapolturev dosing schedule for combination
Participant is receiving injections Q3W (pembrolizumab) or Q4W (nivolumab)	≥ 6 months from Cycle 1 Day 1	Weekly x 7 followed by every Q3W (pembrolizumab) or Q4W dosing (nivolumab)

After 12 participants have been treated under Study Protocol Amendment 4 (amendment that increased the lerapolturev dose and changed to QW injection schedule) and on study approximately 21 days (ie, once n=6 participants per treatment arm receiving lerapolturev QW have completed the dose-limiting toxicity (DLT) evaluation period), an additional safety review will be performed by the DSMC to confirm the safety of lerapolturev with or without anti-PD-1 and/or to make recommendations related to lerapolturev dose and/or schedule adjustments.

Participants receiving the Q3/4W schedule of injections are required to receive the increased lerapolturev dose and will be given the option to change to the QW schedule once Study Protocol Amendment 4 is open at their respective site.

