4.2. EFFICACY

Participants receiving at least one lerapolturev injection and at least 1 post-baseline assessment. If a participant crosses over from monotherapy to combination therapy, then the treatment analyzed will be based on the treatment for that participant at the time of the assessment for the efficacy set.

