5.6.1.2. Primary Efficacy Analysis

The number of participants in each category of best overall response per RECIST v1.1 (confirmed CR, confirmed PR, SD, unconfirmed CR, unconfirmed PR, PD, non-evaluable (NE)) and ORR along with the associated exact 95% two-sided CIs using Clopper Pearson method will be computed within each treatment group and dosing schedule. A participants BOR will be determined based on Table 4.

Supportive data listings will also be provided.

Table 4 Best Overall Response When Confirmation of CR and PR are Required

First Timepoint	Second Timepoint	
Response	Response	Best overall response for ORR
CR	CR	CR
CR	PR	SD, PD or PR ^a
CR	SD	SD
CR	PD	SD
CR	NE or NA	SD
PR	CR	PR
PR	PR	PR
PR	SD	SD
PR	PD	SD
PR	NE or NA	SD
NE CD L	NE	NE

CR = complete response, PR = partial response, SD = stable disease, PD = progressive disease, and NE = not evaluable. a If a CR is truly met at first time point, then any disease seen at a subsequent time point, even disease meeting PR criteria relative to baseline, makes the disease PD at that point (since disease must have reappeared after CR). However, sometimes "CR" may be claimed when subsequent scans suggest small lesions were likely still present and in fact the patient had PR, not CR at the first time point. Under these circumstances, the original CR should be changed to PR and the best response is PR.

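### No rule assigns participants who switch from Q3/4W to QW to one schedule, so Arm 2 switchers can enter the group judged by the 10% lower-limit rule

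*Protocol*

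**What the plan says.** **Populations.** Protocol 8.4 has two schedule-specific efficacy populations: "Participants receiving at least one lerapolturev injection on the QW schedule and at least 1 post-baseline evaluation" and "Participants receiving at least one lerapolturev injection on the Q3/4W schedule and at least 1 post-baseline evaluation". Neither excludes members of the other, and the evaluation need not come after the first QW injection.

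**Switching.** SAP 1.1 states that Q3/4W participants "are required to receive the increased lerapolturev dose and will be given the option to change to the QW schedule"; Protocol 3.1 and 3.1.2 give the same option. Under 3.1.2, those who take the weekly series follow the assessment schedule again from Cycle 1 Day 1.

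**Decision rule.** Protocol 8.2 hypothesises that the combination on QW "will result in an ORR of ≥ 33" percent. Protocol 8.3 and SAP 3.1 call it active "if the lower bound of the 95% CI is above 10" percent, with about 15 participants per arm.

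**SAP.** Protocol 8.5 lets the SAP override the protocol where they differ. SAP 4.2 has one efficacy set, not split by schedule. SAP 5 and 5.6.1 still present results by treatment and dosing schedule, with "ORR along with the associated exact 95% two-sided CIs using Clopper Pearson method". The only attribution rule, in 4.2, concerns participants who cross over from monotherapy to the combination: "the treatment analyzed will be based on the treatment for that participant at the time of the assessment for the efficacy set". SAP 3.2.6 defines one baseline, before any study drug, and ties Cycle 1 Day 1 to the first day of study drug.

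**The concern.** The by-schedule ORR needs every participant to have a schedule, and for switchers neither document supplies one. A programmer could place an Arm 2 switcher in the QW column, the Q3/4W column or both, and each choice would be consistent with some part of the text.

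The choice matters because switchers differ from the participants for whom the QW hypothesis was sized:

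- They enrolled before Amendment 4, whose eligibility changes were meant to remove patients less likely to benefit (Protocol 1.3.2).
- They were stratified on time since prior anti-PD-1/L1 exposure, not on type of resistance (Protocol 8.1).
- They opted for QW after starting treatment, and had to be still receiving injections to do so.
- In the QW column, their tumour change would by default be measured from a baseline that precedes all their Q3/4W treatment.

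At stake is the trial's one activity criterion, which rests on about 15 participants and a threshold of five responses. The study is open-label, so an assignment settled late would be settled with responses already visible.

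**Working it through.** **Inputs.** Two-sided exact Clopper-Pearson 95% interval (SAP 5.6.1.2); pass if the lower limit exceeds 10% (Protocol 8.3); planned Arm 2 QW n = 15 (Protocol 8.3); six participants in Arm 2 on Q3/4W at the December 2021 DSMC meeting (Protocol 9.1.5). For activity on Q3/4W, Protocol 1.2.2.2 reports that "the best anti-tumor responses observed as of the data cutoff have been stable disease" (10 December 2021). The number of Arm 2 switchers, k, is not given, so k = 0 to 6 is an assumed range.

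**Plan's own figure.** For x responses in n, the lower limit is the 0.025 quantile of Beta(x, n − x + 1) and the upper limit is the 0.975 quantile of Beta(x + 1, n − x). For 5/15 this gives 11.82% to 61.62%, which matches the stated 11.8% to 61.6%. For 4/15 the lower limit is 7.79%, so five is the minimum. With n = 15, the chance of passing is 1.27% at a true ORR of 10% and 59.6% at 1/3.

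**Adding k switchers to the QW column.** Now n = 15 + k. The fourth column holds 5 responders among the 15 and assumes no switcher responds. The last three columns give P(X + Y ≥ count needed), with X ~ Bin(15, 1/3) and Y ~ Bin(k, q), where q is the switchers' response rate. The 6% value is the sponsor's ceiling for anti-PD-1 beyond progression (Protocol 1.1), used here only as a low-activity assumption.

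| k | n | Count needed | Lower limit, 5/n | Pass, q = 0 | Pass, q = 6% | Pass, q = 1/3 |
|---|---|---|---|---|---|---|
| 0 | 15 | 5 | 11.8% | 59.6% | 59.6% | 59.6% |
| 1 | 16 | 5 | 11.0% | 59.6% | 60.8% | 66.1% |
| 2 | 17 | 5 | 10.3% | 59.6% | 61.9% | 71.9% |
| 3 | 18 | 6 | 9.7% | 38.2% | 42.0% | 58.8% |
| 4 | 19 | 6 | 9.1% | 38.2% | 43.3% | 64.8% |
| 5 | 20 | 6 | 8.7% | 38.2% | 44.5% | 70.3% |
| 6 | 21 | 6 | 8.2% | 38.2% | 45.8% | 75.1% |

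**The other direction.** Start from 4/15 (7.8%, fail). One responder among one switcher gives 5/16 (11.0%, pass); one among two gives 5/17 (10.3%, pass); one among three gives 5/18 (9.7%, fail). Two responders among six give 6/21 (11.3%, pass).

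**Does other text settle it?** The protocol synopsis analyses by randomised arm and also by dose/schedule; Protocol 8.6 summarises the schedules separately. Neither says where a switcher goes. For treatment crossover, by contrast, the protocol does have rules: run-in crossovers do not count towards the population that establishes the combination's activity (3.1.3), and crossover response is re-baselined and summarised separately (8.5.4). Switching schedule has no counterpart.

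**The case against.** Several points on the other side are sound.

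- **Precedence.** A reader of Protocol 8.4 might infer that switchers will be counted twice. The documents do not support that as the operative rule: the SAP takes precedence and has no separate QW and Q3/4W efficacy populations. What remains is a by-schedule column with no assignment rule.
- **Likely intention.** Protocol 3.1 speaks of participants randomised to each schedule, and 8.1 and 8.4 describe QW recipients by the newer stratification factors, which fits new enrolment rather than switchers. This is a plausible intention, but no analysis text states it.
- **Reach.** A reader might infer that every Q3/4W switcher affects the primary result. Of the 18 participants at the December 2021 meeting, 12 were run-in or Arm 1 monotherapy. They bear on the monotherapy columns, and those who cross over have their own group, with run-in and Arm 1 ORR counted before crossover (SAP 5.6.1). Only combination participants bear on the 10% rule.
- **Size and direction.** All six switching without a response is the extreme case, and one or two non-responding switchers leave five responders sufficient. A reader might infer a bias in favour of the drug, but the arithmetic goes both ways. How long Arm 2 participants were treated before any switch is not reported.
- **Schedule comparison.** Shared participants would blur QW versus Q3/4W, but Protocol 8.3 attaches no formal hypothesis to that comparison.

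These points narrow the concern without removing it: the governing document still lacks the rule.

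**Conclusion.** The concern holds as a missing assignment rule in the SAP that can reach the trial's activity criterion. It does not hold as a demonstration of double counting or of bias in a known direction. Under the readings the text allows, the same 15 QW participants with 5 responses pass with up to two non-responding Arm 2 switchers and fail with three to six; 4 responses fail alone and pass with one responding switcher.

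The size rests on three assumptions: 15 newly randomised Arm 2 QW participants; no Arm 2 participants on Q3/4W beyond the six counted in December 2021; and crossover participants kept in their own group. If no Arm 2 participant switched, the effect is nil.

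**What to change.** In SAP 4.2 and 5:

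1. Assign each participant to one schedule only: the one in force at randomisation, or at first dose for the run-in.
2. Define the set for the 10% rule as participants randomised to Arm 2 on the QW schedule under Amendment 4.
3. Report switchers' post-switch responses separately, and state the baseline against which they are measured.

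Whether to re-baseline at the switch, and whether to stop counting Q3/4W response there, are estimand choices. Either can be defended once switchers are outside the decision set, but the SAP should say which applies.

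Because the SAP takes precedence, Protocol 8.4 need not be amended. The rule should be fixed before ORR is tabulated by schedule. The cost is a few sentences of SAP wording and one derivation flag; any pooled QW group may be smaller.
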